Most relevant to this application is our experience performing hypoglycemic clamp studies while brain activation is studied using magnetic resonance techniques. In our laboratory, we have used continuous arterial spin labeling (CASL) to identify brain regions that are activated in response to insulin-induced hypoglycemia in healthy human subjects (23). Five men and five women (age 29 ± 10 yrs, BMI 23.3 ± 2.1 kg/m², mean \pm SD) participated in this study. CASL images were acquired at euglycemia (99 ± 5 mg/dl) and again during hypoglycemia (52 ± 3 mg/dl) using 2D GE-EPI (labeling time=2500 ms, resolution = $2 \times 2 \times 3$ mm, 100 label/control pairs). In whole brain analysis, increases in regional cerebral blood flow, a measure of neuronal activation, were noted during hypoglycemia relative to euglycemia bilaterally in the medial thalamus, anterior cingulate, and posterior cingulate using BrainVoyager software, as has also been demonstrated by Teves et al using PET (TEVES PNAS 2004). These increases coincided with the peak responses in counterregulatory hormones (glucagon = 110 ± 41 pg/ml, epinephrine = 519 ± 273 pg/ml, norepinephrine = 405 ± 124 pg/ml), providing evidence that activation of these brain regions is involved in the counterregulatory response to hypoglycemia. Focused region of interest analysis of specific regions such as the hypothalamus or amygdala was not performed in this study, but will be performed in the proposed project.

Research Design and Methods:

This study will be a randomized double blind placebo controlled trial involving 20 subjects with type 1 diabetes and hypoglycemia unawareness. Since the time necessary for the effect of naltrexone on our outcome variables to washout after a treatment period is unknown, each subject will serve as their own control and differences between the changes in the outcome measures will be evaluated between groups. The study design is depicted in the figure below.

Subjects

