Subjects between the ages 18 and 65 years of age will be recruited for participation from the University of Minnesota Endocrine Clinic and a registry of volunteers maintained by the investigators. Type 1 diabetes will be defined on clinical grounds. To be categorized as experiencing hypoglycemia unawareness, subjects must first report at the time of initial contact an inability to recognize at least some blood glucose values less than 50 mg/dl during the prior 3 months. At the time of the screening visit, subjects must then be defined as having hypoglycemia unawareness on a Cox questionnaire (24). Exclusion criteria will include concomitant use of acetaminophen, aspirin or ibuprofen (all may increase risk of naltrexone induced liver dysfunction), history of drug or alcohol abuse, current diagnosis or history of psychiatric illness, history of liver disease with elevations in ALT/AST, history of renal insufficiency/failure (creatinine >1.5 mg/dL), pregnancy or breastfeeding, history of seizure or cardiac disease (both of which will increase risk of hypoglycemic clamp), history of stroke, head injury, or other chronic CNS disease, and presence of any characteristics that would preclude placement in the magnet (weight > 300 lbs, presence of metallic implants, etc.).

[figure not shown]
Experimental protocol

The screening visit will occur within two weeks of day zero, which will be the day of the first hypoglycemia study. At the screening visit, informed consent will be obtained and a standardized form will be used to insure subjects meet inclusion/exclusion criteria. Baseline labs for creatinine, ALT, AST, hemoglobin A1c, and CPK will be obtained. The subject will be educated in the use of the continuous glucose monitor and sent home with sufficient supplies to collect data for the seven days before the clamp study on day zero. During this period, subjects will also check their blood glucose before each of three meals and at bedtime and record the values as well as note any episodes in which another person was required to recognize and/or treat hypoglycemia. The continuous glucose monitor display will be blinded to the subject so that it does not influence their diabetes management.

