Subjects will be admitted to the research center the afternoon before the hypoglycemic clamp study on day zero. They will be allowed to take their short acting insulin or a bolus via their pump with their evening meal, but their evening dose of long-acting insulin or their pump will be held after 6 PM. Blood glucose values will then be monitored every 1-2 hours and an intravenous infusion of insulin and/or glucose will be provided to maintain blood sugars between 100-150 mg/dl. Subjects will not be given additional food after their evening meal until the end of the hypoglycemic clamp on day zero.

On the morning of the study, subjects will be transferred to the Center for Magnetic Resonance Research. After their arrival, they will be prepared for clamp study by the placement of one intravenous catheter into one vein in each antecubital fossa for the later infusion of glucose, insulin, and potassium. A third intravenous catheter will be placed retrograde into a vein in the distal leg for later blood sampling. Baseline blood samples for glucose, glucagon, catecholamines, cortisol, and

growth hormone will then be collected no sooner than 30 minutes after catheter placement. At time 0 a constant infusion of insulin will be started at 2.0 mU/kg/min and the subject will be placed into the magnet. Plasma glucose be initially maintained at euglycemia (~100 mg/dl) while the baseline scan is done. Plasma glucose will than be reduced to 50 mg/dl and maintained at this level of glycemia for approximately thirty minutes. During the final 15 minutes subjects will be asked to quantitate their symptoms using a standardized method (25). Blood samples will be obtained every five minutes for measurement of plasma glucose concentration on a nearby analox machine and every twenty minutes for later measurement of glucagon, catecholamines, cortisol, and growth hormone.

Study design. CGMS= continuous glucose monitoring; BG=blood glucose; CASL = continuous arterial spin labeling; hypo= hypoglycemic; safety labs = ALT, AST, Cr, CPK

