This is a pilot study in which a sample size of 20 (10 subjects to receive placebo and 10 subjects to receive naltrexone) was arbitrarily selected to determine how large a sample size will be necessary to determine if naltrexone has an effect on our outcome measures. Each subject will serve as his/her own control and changes in the outcome variables (number of hypoglycemic events defined as number of episodes of hypoglycemia that require the assistance of another to recognize/treat and as minutes during which blood glucose is < 70 mg/dl as measured by continuous glucose monitoring, both over a 7 day period); symptom scores collected during hypoglycemia' and differences in regional blood flow noted between the euglycemic and hypoglycemic conditions for each study), will be compared between pre-treatment and end of treatment periods using Student's t-test with correction for repeated measures. [name] from the Department of Biostatistics at the University of MInnesota will assist in the statistical analyses.

Anticipated problems/potential solutions

The most significant problem we may encounter is that our treatment outcomes will be unaffected by naltrexone treatment. Originally, we intended to focus on the effect of naltrexone on cerebral blood flow as a measure of regional activation during hypoglycemia, but since we are unaware of data that demonstrate naltrexone alters brain activation patterns in addicts, we have broadened our outcome measures to include more clinically relevant information such as frequency of hypoglycemia and symptom scores during controlled hypoglycemia. We are hopeful that naltrexone will have an effect on at least one of the outcome variables and will use the data collected from this pilot to design a larger study.

4. Sinclair JD. Evidence about the use of naltrexone and for different ways of using it in the treatment of alcoholism. *Alcohol Alcohol* 2001;36(1):2-10.

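### Raw minutes below 70 mg/dl over seven days carry no wear denominator and, read literally, overlap the pre-clamp stay; percent of valid outpatient sensor time is a cheap improvement

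*Combined protocol and SAP*

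**What the plan says.** The long-term goal at the start of the protocol and the Statistical analysis section both give the glucose outcome as "minutes during which blood glucose is < 70 mg/dl as measured by continuous glucose monitoring, both over a 7 day period". Neither gives a denominator, a minimum wear or a rule for gaps in the trace.

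Under Experimental protocol, the baseline monitor is to "collect data for the seven days before the clamp study on day zero". The end-of-treatment window is likewise the seven days before the second clamp. On the stay, the same section says "Subjects will be admitted to the research center the afternoon before the hypoglycemic clamp study on day zero". Long-acting insulin or the pump is held after 6 PM, and intravenous insulin and/or glucose keeps glucose at 100-150 mg/dl until the clamp. The second admission follows the same preparation but is placed at night rather than in the afternoon. Nothing says whether the sensor stays on, or is counted, during either stay.

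Research Design and Methods states the comparison: "each subject will serve as their own control and differences between the changes in the outcome measures will be evaluated between groups". Statistical analysis adds that outcomes "will be compared between pre-treatment and end of treatment periods using Student's t-test with correction for repeated measures", and gives the purpose of the 20-subject sample as "to determine how large a sample size will be necessary to determine if naltrexone has an effect on our outcome measures".

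**The concern.** A raw total has no way to separate a minute that was not low from a minute that was not recorded. Unless a rule says otherwise, a subject whose sensor fails for a day appears to have less hypoglycemia. The stay raises a related question. Up to a day of each window may be time in which staff hold glucose well above 70 mg/dl, so it says nothing about free-living hypoglycemia.

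The pilot's product is a set of planning estimates for a larger trial. Variation in wear enters the variance of raw minutes and is carried into that sample size. If the two stays start at different times of day, the counted free-living time also differs between baseline and end of treatment, and the change score absorbs the difference.

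**Working it through.** **The plan's own figure.** The sample size of 20 (10 per arm) is stated to be arbitrary, so there is nothing to reproduce. The documents give no wear, sensor-loss or time-below-70 figures. Every such input below is assumed.

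**1. Effect of lost time on one subject.** The window is 7 × 24 × 60 = 10,080 min. With true fraction low p and fraction lost L unrelated to glucose, raw minutes = 10,080 × p × (1 − L), while percent of valid time stays at p. One fully lost day removes 1/7 = 14%. With L = 20%:

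| p | complete wear | recorded | apparent fall |
|---|---|---|---|
| 4% | 403 | 323 | 81 |
| 7% | 706 | 564 | 141 |
| 10% | 1,008 | 806 | 202 |

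**2. Effect on the next trial's size, equal loss in both arms.** Let W be days worn (7, 6 or 5), c the day-to-day CV (0.8-1.2), w the week-to-week CV within a subject, b the between-subject CV (0.5, 0.8), r the reduction on naltrexone (0, 0.3, 0.5) and f = 1 − r. The relative variance of one window is

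- raw: V = (1 + w²)(1 + c²/E[W] + Var[W]/E[W]²) − 1
- percent: V = (1 + w²)(1 + c²·E[1/W]) − 1

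and the variance of the change, averaged over arms, is (1 + b²)·V·(3 + f²)/2 + r²b²/2. The raw/percent ratio is the sample-size ratio.

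Example: 60/25/15% of windows lose 0/1/2 days, c = 1, r = 0. E[W] = 6.45, Var[W] = 0.5475, E[1/W] = 0.1574.

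- w = 0: raw V = 1/6.45 + 0.5475/6.45² = 0.1682; percent V = 0.1574; ratio 1.069.
- w = 0.3: 0.2733/0.2615 = 1.045.
- w = 0.5: 0.4602/0.4467 = 1.030.

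Over the whole grid:

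| windows losing 0/1/2 days | E[W] | ratio, w = 0 | ratio, w = 0.3-0.5 |
|---|---|---|---|
| 90/8/2% | 6.88 | 1.009-1.029 | 1.005-1.016 |
| 60/25/15% | 6.45 | 1.038-1.116 | 1.022-1.064 |
| equal chances | 6.00 | 1.051-1.152 | 1.030-1.086 |

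Widening c to 0.5-1.5 with w = 0 gives 1.005-1.081, 1.021-1.320 and 1.028-1.417.

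**3. The stay.** No clock times are given. A stay of 12-18 hours is 12/168 = 7.1% to 18/168 = 10.7% of the window; 1 PM to 10 AM would be 21/168 = 12.5%. If the stay is worn, counted, free of lows and of constant length, removing it only rescales the outcome, and the standardized effect is unchanged.

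If its length differs, the change score shifts. For example, take a 9 AM clamp, with admission at 3 PM at baseline (18 h) and 8 PM at end of treatment (13 h). Free-living time is then 150 h and 155 h. At 7% low, that is 630 and 651 min: a rise of 21 min (3%) with no true change. It would be the same in both arms, so it cancels in a between-group comparison of changes when there is no drug effect, but not in a pre/post comparison.

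Starting the window a day earlier, for seven full outpatient days instead of 7 days less 12-18 h, saves the 6-12% more subjects the shorter window would need (w = 0), or 2-9% (w = 0.3-0.5). This comes from more observation, not from removing an error.

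**4. If wear differed by arm.** In 20,000 simulated trials (10 per arm, no drug effect, median 7% low, logit SD 0.5 between and 0.4 within subjects, 10% baseline loss, 960-min stay), end-of-treatment loss on naltrexone/placebo gave:

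| loss | raw difference (min) | raw rejection | percent rejection |
|---|---|---|---|
| 10/10% | +2 | 4.8% | 4.7% |
| 20/10% | −75 | 6.9% | 4.7% |
| 30/10% | −145 | 12.5% | 4.9% |

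With a true 40% reduction and equal 10% loss, power was 35% for raw and 38% for percent.

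**5. Limit of percent time.** If nights are 10% low and days 5.5%, losing half of the night data moves percent from 6.92 to 6.34 (an 8% fall) and raw minutes from 631 to 487 (a 23% fall). Percent time is less affected but not immune.

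**The case against.** The documents never say that lost time is scored as no hypoglycemia. They are silent, and a careful analyst might scale to worn time anyway. That stands: the point is an inference from an unscaled definition with no rule beside it. Equally, nothing says the sensor is worn or counted during the stay, so the overlap is a literal reading of the window and not a described practice. A constant overlap would do no harm to the standardized effect.

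The gain is also small beside the pilot's own imprecision. With 18 degrees of freedom, a normal-theory 95% interval for the variance runs from 0.57 to 2.19 times the estimate, so a refinement of a few percent will seldom change the planned size. Treating days as independent exaggerates the gain; a week-to-week CV of 0.3-0.5 roughly halves the upper end. These objections fix the size of the point. They do not favor raw minutes, since the alternative costs almost nothing.

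A reader might infer that the naltrexone comparison is biased. The documents do not support that: nothing indicates that wear will differ by arm, and the 12.5% rejection rate above is hypothetical. Nor is the planned t-test shown to be invalid; with equal loss its rejection rate was 4.8%.

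A reader might also extend the complaint to the assisted-episode count. The documents give no event rate. The plan already provides 210 untreated subject-days (20 baseline weeks and 10 placebo weeks). At assumed rates of 1, 3 and 5 per subject-year with between-subject variance 1, the chance of no untreated event is 57%, 19% and 7%. How far this matters depends on an unknown rate, and no change is proposed here.

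**Conclusion.** The point holds as a cheap improvement to an outcome definition, not as a flaw that invalidates the comparison. Raw minutes leave lost sensor time and the pre-clamp stay undefined, and the afternoon and night descriptions of admission leave open whether the two windows cover the same free-living time.

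For day-to-day CV 0.8-1.2 and week-to-week CV 0-0.5, sizing the next trial on raw minutes would need about 0.5-3% more subjects under light loss and 2-15% more under heavier loss. The further benefit is protection if wear differs by arm or period, which the documents do not show. All of this rests on assumed loss patterns and on loss unrelated to glucose.

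The change does not give the pilot adequate power. Ten per arm detects about 1.25 SD (normal) or 1.32 SD (t) at an assumed 80% power and two-sided 5% level.

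**What to change.** In the outcome definition and the Statistical analysis section:

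- Define the glucose outcome as the percentage of valid outpatient sensor time below 70 mg/dl. Keep raw minutes as a descriptive summary.
- End both windows at the same clock time on the day before each clamp, at or before the earliest admission. Reconcile the afternoon and night descriptions of admission.
- Prespecify a minimum wear that includes night hours, and treat a window below it as missing. A total-hours rule alone is not enough: with 150-156 outpatient hours, losing all six 8-hour nights still leaves 102-108 hours.
- Report wear by arm and by period.
- Keep the planned comparison of changes between groups.
- Optionally, start each window one day earlier to keep seven outpatient days.

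The cost is wording. Without the earlier start, about 7-11% of sensor time (12-18 of 168 hours) is given up. With it, screening must fall at least 8 days before day zero, which fits "The screening visit will occur within two weeks of day zero", and supplies must last one more day. The end-of-treatment window would then open about day 20 of 28, still after the 14-day visit. A minimum-wear rule may lose a subject from an arm of ten. The documents give no wear data from which to estimate how often.

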NCT01053078

Naltrexone and Hypoglycemia in Type 1 Diabetes

Protocol Approval Date: August 17th, 2012

PI: [name]

Hypoglycemia unawareness is a limiting factor in the treatment of type 1 diabetes and is a very difficult problem to reverse. Using positron emission tomography (PET), Dunn et al have recently demonstrated that patients with type 1 diabetes and hypoglycemia unawareness display a brain activation pattern during hypoglycemia that resembles the activation pattern seen following the administration of an addictive substance such as cocaine (1). In this response, the amygdala and hypothalamic regions associated with stress were less activated and the ventral striatum region associated with motivation and the lateral orbitofrontal cortex region associated with reward were not activated as strongly during hypoglycemia in the unaware compared to the aware subjects. These observations raise the question of whether one reason hypoglycemia unawareness is so difficult to reverse is that it is rewarding and not perceived as a stress to the patient, much like the response an addict has to a drug upon which he has grown dependent. If so, therapies applied to the treatment of addictions might provide a novel approach to the treatment of hypoglycemia unawareness in type 1 diabetes. One such therapy could be the orally administered non-addicting opioid antagonist naltrexone that has been shown to be effective in the treatment of many addictions (2-4).

The long-term goal of this project is to test the hypothesis that naltrexone therapy in subjects with type 1 diabetes and hypoglycemia unawareness will:

- reduce the number of hypoglycemic events (defined as number of episodes of hypoglycemia that require the assistance of another to recognize/treat and as minutes during which blood glucose is < 70 mg/dl as measured by continuous glucose monitoring, both over a 7 day period),
- improve recognition of hypoglycemia during experimental conditions, and
- reduce activation in the ventral striatum and lateral orbitofrontal cortex and increase activation in the amygdala and hypothalamus during hypoglycemia.

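### CGM minutes below 70 mg/dl are to be tested as raw change with no baseline adjustment; ANCOVA on the same minutes gains power if the effect is proportional and costs about 2 points at most if it is additive

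*Combined protocol and SAP*

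**What the plan says.** The opening hypotheses list first that naltrexone will "reduce the number of hypoglycemic events", defined in two ways, each over 7 days: assisted episodes and "minutes during which blood glucose is < 70 mg/dl as measured by continuous glucose monitoring". The Statistical analysis section sends both, together with symptom scores and regional blood flow, through one method: changes are compared "using Student's t-test with correction for repeated measures". The correction is not defined. No transformation, rank method, covariate or check of distribution is named.

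The contrast is worded in two ways. Research Design and Methods says that "differences between the changes in the outcome measures will be evaluated between groups". Statistical analysis says the outcomes "will be compared between pre-treatment and end of treatment periods" and does not restate the comparison between arms. Read together, the likeliest analysis is a two-sample t-test on raw change, naltrexone against placebo.

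On size, "a sample size of 20 (10 subjects to receive placebo and 10 subjects to receive naltrexone) was arbitrarily selected". The stated purpose is to learn how large a later trial must be. No power target is set.

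**The concern.** Weekly minutes below a threshold lie between 0 and 7 × 24 × 60 = 10,080. If the values are skewed and treatment reduces them in proportion, a heavily exposed subject changes by many more minutes than a lightly exposed one. With 10 per arm, one or two such subjects can then dominate both the mean and the SD of raw change.

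Subtracting baseline also fixes the pre-post slope at 1. When the true slope is smaller, baseline noise is added to the outcome instead of being removed from it. ANCOVA estimates that slope from the data.

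At stake are the precision of the treatment comparison and the stability of the SD that the pilot is meant to hand to the next trial.

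**Working it through.** **No figure to reproduce.** The sample size of 20 was not calculated. For orientation, 10 per arm at two-sided 0.05 (assumed) gives power of 18.5%, 40% and 56% at standardised effects of 0.5, 0.8 and 1.0. Reaching 80% needs about 1.33.

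**Inputs.** From the documents: 10 per arm, a 7-day window before and at the end of treatment, and a t-test on change. Assumed: lognormal minutes with median 600 per week, log-SD σ from 0.5 to 1.1, log-scale correlation ρ of 0.4 or 0.7, treatment halving the minutes, and no dropout.

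**By hand, for σ = 0.8 and ρ = 0.7.** Let V be the variance of raw minutes without treatment.
- Mean = 600·exp(σ²/2) = 600 × 1.377 = 826. A halving removes 413 minutes on average.
- V = 600²·exp(σ²)·(exp(σ²) − 1) = 360,000 × 1.8965 × 0.8965 ≈ 612,000, so the SD is 782.
- Raw-scale correlation = (exp(ρσ²) − 1)/(exp(σ²) − 1) = 0.565/0.8965 = 0.63.
- Variance of change: placebo 2(1 − 0.63)V = 0.74V; naltrexone (1 + 0.25 − 2 × 0.5 × 0.63)V = 0.62V. The average is 0.68V.
- ANCOVA: common slope = (0.63 + 0.315)/2 = 0.47. Residual variance: placebo (1 + 0.47² − 2 × 0.47 × 0.63)V = 0.63V; naltrexone (0.25 + 0.47² − 2 × 0.47 × 0.315)V = 0.17V. The average is 0.40V.
- Standardised effect: change 413/(782 × √0.68) = 413/645 = 0.64; ANCOVA 413/(782 × √0.40) = 413/495 = 0.83.

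So baseline adjustment alone cuts the error variance to 0.40/0.68 = 59% of its value. Simulated power in this case (33% and 52%) is above what normal theory suggests at 0.64 and 0.83, because many small samples miss the long tail. The ordering is the same.

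**Simulated power for a halving.** Separate runs agree to within one or two points.

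| log-SD | correlation | t-test on change | raw ANCOVA | rank ANCOVA | log ANCOVA |
|---|---|---|---|---|---|
| 0.5 | 0.7 | 75% | 94% | 95% | 98% |
| 0.5 | 0.4 | 52% | 81% | 86% | 88% |
| 0.8 | 0.7 | 33% | 52% | 64% | 69% |
| 1.1 | 0.4 | 11% | 17% | 28% | 29% |

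Relative to raw ANCOVA, the t-test on change loses (94 − 75)/94 = 20%, (81 − 52)/81 = 36%, (52 − 33)/52 = 37% and (17 − 11)/17 = 35%. In the third row, baseline adjustment supplies 52 − 33 = 19 of the 64 − 33 = 31 points gained by rank ANCOVA. A separate simulation (CV 0.8, correlation 0.5) gave 31% for the t-test on change, 51% for raw ANCOVA and 64% for log ANCOVA.

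**Additive effect.** Here baseline minutes were kept skewed (log-SD 0.5 to 0.8), but treatment removed a fixed number of minutes, with symmetric within-subject error of SD 100 to 150 (assumed). The t-test on change had 53-57% power and raw ANCOVA was within about 2 points of it. Rank ANCOVA lost about 7-17 points and log ANCOVA 13-22.

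**Type I error.** It was 3-5% in the null scenarios, so the planned test is not anticonservative.

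**Sizing the next trial.** For a fixed effect, the next sample size is proportional to the variance of change. The ratio of the 90th to the 10th percentile of the pilot's pooled variance was 3.4-4.0 at log-SD 0.5 and 6.0-7.0 at log-SD 0.8 on the raw scale, against 2.4 on the log scale. The last figure is what normal theory gives on 18 degrees of freedom.

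**The case against.** The strongest reply is that the assumptions create the loss. Only the bound at zero follows from the documents; the skew, the proportional effect and its size are supplied here. A lognormal model with a multiplicative effect favours log-scale methods by construction. That stands, and it is why the rank or log analysis should not become the main one: with an additive effect both lose power, even when minutes are skewed. It does not defend the unadjusted change score, because raw ANCOVA was better than the t-test or within 2 points of it in every scenario.

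Second, a pilot of arbitrary size has no power to protect. This stands as far as it goes, but the pilot's product is the input for a later sample size, and an unstable SD harms that directly.

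Third, the analysis section can be read as a pre-post comparison within each arm. On that reading the loss against a log-scale analysis, for a halving at correlation 0.5, is smaller: 2% at CV 0.5, 22% at CV 0.8 and 32% at CV 1.0. But that reading leaves out the placebo comparison that the design section calls for.

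A reader might go further and infer that the plan forfeits a third of the power on its main clinical outcome. The documents support neither half of that. No main outcome is designated, and no fixed fraction can be derived without an SD, a correlation and an effect. With mild skew (log-SD 0.3), the t-test on change detects a halving 94-99% of the time.

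**Conclusion.** The point holds as a question of efficiency. The planned t-test on raw change is valid but ignores what baseline minutes can contribute. Under lognormal minutes and a halving, replacing it by ANCOVA on the same raw minutes raises power from about 11-75% to 17-94%. Under an additive effect it changes power by about 2 points at most. These figures rest on an assumed median of 600 minutes per week, log-SD 0.5 to 1.1, correlation 0.4 to 0.7 and two-sided 0.05; none is in the documents.

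Moving to ranks or logs adds more if the effect is proportional (rank ANCOVA 28-95%) and costs about 7-22 points if it is additive. Which of these applies is not known before the pilot, so the scale belongs in sensitivity analyses. It would be wrong to conclude that the t-test inflates false positives, or that skew alone explains the gap: in the middle scenario, 19 of the 31 points come from baseline adjustment.

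**What to change.** In Statistical analysis, before unblinding:

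1. Replace the t-test on change, for minutes below 70 mg/dl, with a between-arm ANCOVA of end-of-treatment minutes adjusted for baseline minutes. Report the adjusted difference in minutes with its confidence interval. State that the contrast is naltrexone against placebo, so that it agrees with Research Design and Methods.
2. Prespecify two sensitivity analyses: a rank ANCOVA, and a baseline-adjusted ratio of geometric means from log minutes plus a stated constant.
3. Report the log-scale SD and the pre-post correlation beside the raw SD, for sizing the next trial.
4. Compare assisted-episode counts between arms by a permutation test. A 7-day count in 10 subjects per arm is likely to be sparse, although the documents give no rate.

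The cost is one degree of freedom, a few lines of code and no new data. The rank and log results may differ from the main result, particularly if the effect is additive, so the plan should say in advance that the raw-minutes ANCOVA is the one to be interpreted.
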